5.1. Inclusion Criteria

Participants are eligible to be included in the study only if all of the following criteria apply at screening and/or enrollment:

Age

1. Participant must be 18 to 65 years of age inclusive, at the time of signing the informed consent.

Type of Participant and Characteristics

- 2. Overtly healthy for Part A and Part C as determined by medical evaluation, including medical history, physical examination, laboratory tests, and cardiac monitoring (including ECGs).
 - a. To qualify as Japanese for the purpose of this study, the participant must be first-generation Japanese, defined as the participant's biological parents and all of the participant's biological grandparents must be of exclusive Japanese descent, and must have been born in Japan.
 - b. To qualify as Chinese for the purpose of this study, the participant must be, at a minimum, third-generation Chinese, defined as all 4 of the participant's biological grandparents must be of exclusive Chinese descent and born in China.
- 3. Have clinical laboratory test results within the normal reference range for the population or investigative site or results with acceptable abnormalities that are judged to be not clinically significant by the investigator.
- 4. Have venous access sufficient to allow for blood sampling and administration of IP for IV administration as per the protocol.
- 5. Are reliable, willing to make themselves available for the duration of the study, and willing to follow study procedures.

Body Mass Index and Weight

6. Have a body mass index of 18.0 to 32.0 kg/m^2 , inclusive, for Parts A and C, and 18.0 to 38.0 kg/m^2 , inclusive, for Part B.

Sex and Contraceptive/Barrier Requirements

- 7. Male or Female
 - a. Male participants:

- i. Refer to Appendix 4 (Section 10.4) for definitions and additional guidance related to contraception.
- b. Female participants:
 - ii. WNOCBP may participate in this trial. Refer to Section 10.4 for definitions and additional guidance related to contraception.

Informed Consent

8. Are capable of giving signed informed consent as described in Appendix 1 (Section 10.1.3), which includes compliance with the requirements and restrictions listed in the informed consent form (ICF) and in this protocol.

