- 27. had any malignancy within the past 5 years. Exceptions: successfully treated basal cell skin carcinoma or squamous cell skin carcinoma with no evidence of recurrence or metastatic disease within the 3 years prior to baseline.
- 28. current smoker using >10 cigarettes or other tobacco products per day and are unable/unwilling to stop smoking tobacco products while in the study unit and have a positive cotinine test.
- 29. are regular users of known drugs of abuse and/or have positive findings on urinary drug tests at screening, OR an average weekly alcohol intake that exceeds 21 units per week (males) or 14 units per week (females), OR are unwilling to stop alcohol consumption during study visits/time in the research unit (1 unit of alcohol = 12 oz or 360 mL of beer, 5 oz or 150 mL of wine, and 1.5 oz or 45 mL of distilled spirits).
- 30. are regular users of cannabis (legal or medical).
- 31. have received blood products within 6 months before screening or donated blood of more than 500 mL within the previous 30 days of study screening.
 - a. For Chinese participants:
 - i. Have donated blood of more than 400 mL within the previous 30 days of study screening.
- 32. have known hypogammaglobulinemia or a screening serum immunoglobulin G or immunoglobulin M below the reference range.

33. have a history of a primary immunodeficiency, splenectomy, or any underlying condition that predisposes the participant to infection that, in the opinion of the sponsor or investigator, poses an unacceptable risk to the participant.

- 34. have presence of significant uncontrolled cerebro-cardiovascular (for example, myocardial infarction, unstable angina, hypertension, moderate-to-severe [New York Heart Association Class III/IV] heart failure, or cerebrovascular accident), respiratory, hepatic, renal, gastrointestinal, endocrine, hematologic, neurologic or neuropsychiatric disorders, or abnormal laboratory values at screening that, in the opinion of the sponsor or investigator, pose an unacceptable risk to the participant if participating in the study or interfering with the interpretation of data.

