ECGs will be interpreted by a qualified investigator (the physician or qualified designee) at the site soon after the time of ECG collection as possible, and ideally while the subject is still present, to determine whether the subject meets entry criteria at the relevant visit(s) and for immediate subject management should any clinically relevant findings be identified.

If a clinically significant quantitative or qualitative change from baseline is identified after the enrollment, the investigator will assess the participant for symptoms (for example, palpitations, near syncope, and syncope) to determine whether the participant can continue in the study. The investigator or qualified designee is responsible for determining if any change in participant management is needed and must document review of the ECG as soon as possible after the time of collection from at least one of the replicate ECGs from each time point.

Triplicate digital ECGs will be electronically transmitted to a central ECG laboratory designated by Lilly. The central ECG laboratory will perform a basic quality control check (for example, demographics and study details) and then store the ECGs in a database. At a future time, the stored ECG data may be overread at the central ECG laboratory for further evaluation of machine-read measurements or to meet regulatory requirements.

The machine-read ECG intervals and heart rate may be used for data analysis and report writing purposes, unless a cardiologist's overread of the ECGs is conducted prior to the completion of the final study report (in which case the overread data would be used).

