10.6 Safety and Tolerability Assessments

10.6.1 Adverse events

Where changes in severity are recorded in the Case Report Form (CRF), each separate severity of the AE will be reported in the listings, only the most severe will be used in the summary tables. A pre-existing condition is defined as a condition that starts before the participant has provided written informed consent and is ongoing at consent. A non-treatment emergent AE is defined as an AE which starts after informed consent but prior to dosing. A TEAE is defined as an AE which occurs postdose or which is present prior to dosing and becomes more severe postdose.

All AEs will be listed. All TEAEs will be summarized by part, treatment, severity, and relationship to the study drug. The frequency (the number of AEs, the number of participants experiencing an AE and the percentage of participants experiencing an AE) of TEAEs will be summarized by part, treatment, Medical Dictionary for Regulatory Activities (MedDRA) (version is documented in the Data Management Plan [DMP]) system organ class and preferred term. The summary and frequency AE tables will be presented for all causalities and those considered related to the study drug by the investigator. Any SAEs will be listed by treatment group. For Parts B and C, AEs by day of onset will be presented, where onset time is based on the last dose received.

Discontinuations due to AEs will be listed.

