10.6.5 Electrocardiogram (ECG)

For Part A, ECGs will be collected in triplicate at all time points excluding screening and the last scheduled follow-up visit. These ECG data will be presented as below. For Parts B and C, ECGs will be presented if collected in triplicate. Otherwise, ECGs from Parts B and C will not be presented, and any clinically significant findings from ECGs will be reported as an AE.

The ECG data will be obtained directly from the 12-lead ECG traces. These data include the PR, QT, QRS duration and heart rate. In addition, QT interval corrected using Fridericia's formula (QTcF) will be calculated as follows:

$$QTcF = \frac{QT}{\sqrt[3]{60/HR}}$$

The ECG data will be summarized by part, treatment and time point together with changes from baseline, where baseline is defined as the mean of the triplicate Day 1 predose. Figures of mean ECG data and mean changes from baseline will be presented by part and treatment. The frequency of participants with a maximum increase from baseline in QTcF interval will be summarized by part, and for each treatment according to the following categories: >30 ms and >60 ms. In addition, the frequency of participants with QTcF postdose values, according to the following categories: >450 ms, >480 ms and >500 ms, will be summarized by treatment.

CONFIDENTIAL Protocol Reference: J4L-MC-KMAA

Concentration-QTc Analysis (Part A only)

A plasma LY3872386 concentration-QTc analysis will be performed to assess the relationship between changes from baseline (mean of Day 1 predose assessments) in QTcF (Δ QTcF) and plasma LY3872386 concentrations across all treatments. IV and SC data will be pooled.

A linear mixed effects analysis model will be employed with ΔQTcF as the response variable, time-matched LY3872386 concentration as the explanatory variable (0 for PBO), centered baseline QTcF as an additional covariate, treatment (PBO=0 or LY3872386 =1), PK profile day, time (nominal time postdose), and the interaction between PK profile day and time as fixed effects, and a random intercept and concentration slope per participant. The model⁴ will have the form:

$$\Delta ECG_{i,j,k,l} = (\theta_0 + \eta_{0,i}) + \theta_1 TRT_j + (\theta_2 + \eta_{2,i})C_{i,j,k,l} + \theta_{3,k} DAY_k + \theta_{4,l} HOUR_l + \theta_{5,k,l} DAY_k \times HOUR_l + \theta_6 (ECG_{i,j,k=1,l=0} - \overline{ECG_{k=1,l=0}}) + \varepsilon_{i,j,k,l},$$

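### The absolute QTcF table ignores baseline, so a participant above 450 ms before dosing looks the same as one who crossed 450 ms afterwards

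*SAP*

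**What the plan says.** SAP Section 10.6.5 plans two categorical QTcF summaries.

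- **Change from baseline.** "The frequency of participants with a maximum increase from baseline in QTcF interval will be summarized by part" and by treatment, "according to the following categories: >30 ms and >60 ms".
- **Absolute level.** By treatment, "the frequency of participants with QTcF postdose values, according to the following categories: >450 ms, >480 ms and >500 ms".

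The same section supplies a baseline for the change summaries: "where baseline is defined as the mean of the triplicate Day 1 predose". The absolute categories do not use it. They carry no qualifier such as new or treatment-emergent, no baseline column and no shift layout.

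The ECG summaries certainly apply to Part A. They apply to Parts B and C only if triplicate ECGs are taken there.

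None of the eligibility criteria, numbered 1 to 52 in Protocol Sections 5.1 to 5.2.1, contains a QT or QTc value. Criterion 2 asks for overt health judged partly on ECGs (Parts A and C). Criterion 34 excludes those who "have presence of significant uncontrolled cerebro-cardiovascular" or other listed disease that the sponsor or investigator thinks poses an unacceptable risk. Criterion 38 leaves general suitability to judgement. The only QTc numbers in the protocol are the on-study discontinuation considerations in Section 7.1.3.1.

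**The concern.** A count of post-dose values above a threshold is usually read as a sign of what happened after dosing. Here it mixes two groups: participants whose QTcF rose through the threshold, and participants who were above it all along. With no numeric entry limit, the second group can be enrolled.

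Part A has eight active dose rows, so one such participant can put a count in a dose row that has nothing to do with the drug. A reader of the summary tables could not tell.

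The SAP separates old from new elsewhere. In Section 10.6.1 an adverse event already there before dosing is treatment-emergent only if it is one "which is present prior to dosing and becomes more severe postdose". The absolute QTcF table makes no comparable distinction.

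**Working it through.** The plan states no expected outlier rate, QTcF mean or SD, and the cohort sizes are blacked out, so there is no figure to reproduce. Two checks were made.

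**1. Can the planned summary tables separate the cases?** Three hypothetical participants:

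| Participant | Predose | Highest post-dose | Change | >450 | >480 | >30 | >60 |
|---|---|---|---|---|---|---|---|
| A | 455 ms | 455 ms | 0 | yes | no | no | no |
| B | 440 ms | 455 ms | +15 | yes | no | no | no |
| C | 452 ms | 478 ms | +26 | yes | no | no | no |

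All three give the same entries. A was already above, B crossed, and C was already above and worsened. Reading the two summaries together does not separate them.

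**2. How much could this matter with no drug effect?**

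Assumptions, none taken from the documents:

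- population mean QTcF μ = 400, 410 or 420 ms
- between-person SD σb = 15 or 20 ms
- SD of a triplicate mean within a person σw = 6 or 8 ms
- an illustrative group of 6
- no screening out of high values
- the table flags any post-dose triplicate mean above the threshold.

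Eight post-dose triplicates are used. The Part A schedule has seven, leaving out the last follow-up visit, where a single ECG is taken; Protocol Section 8.2.3 adds a reading at about 6 hours in the IV cohorts.

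Model: person mean t ~ N(μ, σb²), baseline b = t + e₀, post-dose yⱼ = t + eⱼ for j = 1 to 8, and every e ~ N(0, σw²).

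- Planned count: max yⱼ > 450.
- New crossing: max yⱼ > 450 and b ≤ 450.
- Share already above = (planned − new) / planned.

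There were 1,000,000 simulated participants in each of 12 scenarios. The rows below are all four at 410 ms and those at the extremes (% of participants, except the last column):

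| μ / σb / σw | Baseline >450 | Planned count | New crossing | Share already above |
|---|---|---|---|---|
| 400 / 15 / 6 | 0.10 | 0.37 | 0.29 | 22% |
| 400 / 15 / 8 | 0.17 | 0.74 | 0.63 | 15% |
| 410 / 15 / 6 | 0.66 | 2.09 | 1.53 | 27% |
| 410 / 15 / 8 | 0.92 | 3.51 | 2.80 | 20% |
| 410 / 20 / 6 | 2.78 | 6.13 | 3.57 | 42% |
| 410 / 20 / 8 | 3.18 | 8.27 | 5.43 | 34% |
| 420 / 20 / 6 | 7.53 | 14.57 | 7.44 | 49% |
| 420 / 20 / 8 | 8.18 | 18.30 | 10.73 | 41% |

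Worked row (410 / 20 / 6): (6.13 − 3.57) / 6.13 = 42%. Its baseline column agrees with the closed form: (450 − 410) / √(20² + 6²) = 40 / 20.88 = 1.92, an upper tail of 2.8%.

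Across all 12 scenarios the share runs from 15% to 49%. A second set of assumptions (mean 410 to 420, SD 16 to 18, within-person SD 5 to 9, seven post-dose triplicates) gives 21% to 50%.

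The planned count at >480 ms is at most 0.9% of participants, and at >500 ms at most 0.05%.

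For a group of 6 with mean 410 ms, the chance of at least one participant is 1 − (1 − p)⁶:

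- planned count, p = 2.09% to 8.27%: 12% to 40%
- new crossings only, p = 1.53% to 5.43%: 9% to 29%
- above both before and after dosing, p = 2.09 − 1.53 (unrounded 0.55%) to 8.27 − 5.43 (2.84%): 3% to 16%.

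**The case against.** The strongest reply is that the table reports levels, and that neighbouring outputs deal with drug effect. Section 10.6.5 also gives changes by treatment and time point, the >30 and >60 ms categories, and a concentration-QTc model on change from baseline that adjusts for baseline. Section 10.1 promises listings of all databased data, so a flagged participant's predose value can be looked up. This stands in part. The listings do allow the distinction, and in small cohorts the look-up is easy. The summaries do not: the change categories fail on participants A to C above, and the model addresses the mean effect, not who crossed. Pooled placebo shows a background rate but cannot correct a chance baseline imbalance in one dose row.

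Several other replies limit the weight of the point:

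- Investigators read ECGs at entry and may in practice keep out high values. The simulation ignores this.
- The SAP's TFL shell document was not available and might already have a baseline row, although the SAP text does not require one.
- Most no-effect flags come from participants not above 450 ms at baseline (about 50% to 85%, the complement of 15% to 50%). These are chance crossings over repeated readings, and a baseline condition does not remove them.
- The adverse-event comparison is imperfect. That rule keeps a pre-existing event that worsens, whereas counting only new crossings would drop participant C. Section 10.6.3 flags out-of-range laboratory values without regard to baseline.

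Two stronger readings are tempting. A reader might infer that the table will show a false drug signal at all three thresholds. The documents do not support that: the effect depends on enrolling someone above a cut-off, and it nearly vanishes above 450 ms under the assumptions used. A reader might also infer that new-onset counts should replace the planned count. That would discard information, as participant C shows.

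**Conclusion.** The point holds as a minor gap in a descriptive safety table. The text is clear on both premises: the absolute categories have no baseline condition, and no numeric QTc entry limit exists. Someone above a threshold both before and after dosing is therefore counted in the dose row, and the summaries cannot separate that from a post-dose crossing.

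The size is conditional. At >450 ms, roughly 15% to 50% of no-effect flags would have been above the threshold at baseline, given the assumed means, SDs and number of readings. The per-group chances rest also on the assumed group of 6. If no enrolled participant exceeds 450 ms at baseline, the planned and new-onset counts are identical.

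ECG outliers are not a primary or secondary endpoint, and SAP Section 10.6.15 plans no inferential safety analysis, so nothing inferential is invalidated. Whether the protocol ought to have a QTc entry limit is a clinical matter outside this point.

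**What to change.** Keep the count of all participants with post-dose QTcF above each threshold, and keep the >30 and >60 ms change categories. Add to SAP Section 10.6.5, for each threshold and each treatment including pooled placebo:

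- the number whose baseline triplicate mean is already above the threshold
- the number newly above it after dosing, with those at or below it at baseline as denominator.

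A shift table of baseline category (≤450, >450 to 480, >480 to 500, >500 ms) by highest post-dose category gives the same information. It keeps participants already above 450 ms in view and shows any move to a higher band. A rise within one band, such as 452 to 478 ms, would still have to be read from the listing.

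The cost is one or two SAP sentences and a small change to one table shell. All the data are already collected, and dosing, stopping rules and eligibility are untouched.

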Urinalysis	X	X		X	X		X		X		X		X	X			X	X	

			P	art A: S	ingle	-Asce	ending	g Dose	of LY	387238	6 in He	ealthy I	Particip	ants					
Procedures / Assessments	Screen	ning		Trea	tmen	t Per	iod						Follo	ow-up				E D	Comments
Visit Number	V1			V	72					V 801	V 802	V 803	V 804	V 805	V 806	V 807	V 808		
Study Day	C	C																	
Pharmacogenetics			Р																CCI
Immunogenicity			P								X		X		X		X	X	
LY3872386, total antibody, and LY3558533 (free payload) concentration (PK)			P, EOI, 3 hr, 6 hr, and 12 hr	X	X	X	X	X	X	X	X	X	X	X	X	X	X	X	
			Р	X		X			X		X	X	X	X	X	X	X	X	
OO!			Р	X		X			X		X	X	Х	X	X	Х	X	X	
			P	X					X		X						X	X	
			P	X		X			X		X		X		X		X	X	
			P			X			X		X		X		X		X	X	
		X							Х		X	X	X		X		X	X	

			P	art A: Si	ingle-	-Asce	ending	Dose	of LY	387238	66 in He	ealthy I	Particip	ants					
Procedures / Assessments	Screen	iing		Trea	tmen	t Per	iod						Follo	ow-up				E D	Comments
Visit Number	V1			V	72					V 801	V 802	V 803	V 804	V 805	V 806	V 807	V 808		
Study Day	C																		
Cortisol		X	P and 12 hr	X	X	X	X	X			X			X					CCI
CCI			X	X	X	X	X	X											
CCI		X							X		X		X		X		X	X	

			P	art A: S	ingle-	-Asce	nding	Dose	of LY	387238	6 in He	althy F	articip	ants					
Procedures / Assessments	Screen	ning		Trea	tmen	t Peri	od						Follo	w-up				E D	Comments
Visit Number	V1			V	V 2					V 801	V 802	V 803	V 804	V 805	V 806	V 807	V 808		
Study Day	C																		
Ocular pressure, visual acuity, and cataract evaluation	Х										X			X			X	X	CCI

Abbreviations: AE = adverse event; CRU = clinical research unit; CCl CXR = chest x-ray; d = day(s); ECG = electrocardiogram; ED = early discontinuation; EOI = end of IV infusion or subcutaneous dose administration; FSH = follicle-stimulating hormone; hr = hours; I/E = inclusion/exclusion; IP = investigational product; min = minutes; P = predose before IP administration; CCl PK = pharmacokinetic; SAD = single-ascending dose; TB = tuberculosis; TST = tuberculin skin test; V = visit.

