LY3558533 (Payload)

General toxicity

One-month repeat-dose toxicology studies with LY3558533 were conducted in rats and monkeys. There were no adverse findings in either study, up to the highest dose tested. Observed effects were generally consistent with known effects of GC in animal species.

Safety pharmacology

In an in vitro hERG assay, the IC₅₀ for the inhibitory effect of LY3558533 on hERG potassium current was estimated to be greater than μ M, an unbound plasma concentration that would not be achievable in humans.

Genotoxicity

LY3558533 was evaluated for mutagenicity in an Ames assay, and for effects on chromosomes in human TK6 cells and in rats. There were no effects observed in any study, up to the highest concentration or dose tested.

Nonclinical Drug Disposition and Pharmacokinetics

LY3872386 (ADC)

- The PK of LY3872386 (fully intact DAR4) and total antibody (includes unconjugated Ab and Ab conjugated to at least 1 payload) were evaluated in PK study in monkeys after IV and SC doses of LY3872386. The plasma clearance of LY3872386 or total antibody was low in monkeys based on comparison to hepatic blood flow. The relative SC bioavailability of LY3872386 was approximately 6%.
- The TK of LY3872386, total antibody, and LY3558533 (unconjugated payload) were evaluated in the 3-month GLP toxicology study. The exposure to LY3872386 and total antibody increased with increasing dose in an approximately dose-proportional manner on Day 1 and in a greater than dose-proportional manner on Day 85. The exposure to LY3558533 increased in an approximately dose-proportional manner. Based on mean exposures including all animals, no to minimal accumulation of LY3872386, total

antibody, or LY3558533 (unconjugated payload) was observed following repeat SC or IV administration of LY3872386. ADA positive response was detected in multiple animals after repeat SC dosing and contributed to the decrease in exposure of LY3872386 and total antibody on Day 85. The presence of ADA had no impact on the exposure to LY3558533 (unconjugated payload).

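### The concentration-QTc model uses intact ADC concentration only; a separate supportive model on the free payload, measured on the same schedule, would cover a payload effect that peaks later than the ADC.

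*SAP*

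**What the plan says.** SAP 10.6.5 plans the following for Part A: "A plasma LY3872386 concentration-QTc analysis will be performed". The response is change from baseline in QTcF, with "time-matched LY3872386 concentration as the explanatory variable", set to 0 for placebo. The reported slope, the predictions at geometric mean Cmax, the residual plot and the hysteresis plot all use that analyte. The section extends the analysis to RR, HR, PR and QRS, but not to a second analyte. Protocol 9.3.5.1.1 also names only LY3872386.

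Protocol 2.2 shows what the analyte is: "The PK of LY3872386 (fully intact DAR4) and total antibody" were evaluated as separate quantities in monkeys. So LY3872386 means the conjugate carrying all four payloads.

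The only hERG assay described is on the payload. In Protocol 2.2 the IC50 "for the inhibitory effect of LY3558533 on hERG potassium current" was above a redacted value, called "an unbound plasma concentration that would not be achievable in humans".

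Payload data will exist. The Part A Schedule of Activities (Protocol 1.3.1) has one PK row for ADC, total antibody and payload, and every postdose ECG visit in that table also has a PK sample. Protocol 8.4.3 plans the payload assay and SAP 10.3.1 plans its PK parameters. Payload Cmax and AUC are secondary endpoints, and Protocol 2.3 lists systemic glucocorticoid exposure from the payload among the key safety concerns.

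**The concern.** If the product affected repolarization through the payload, the effect would follow payload concentration. A same-time linear model on ADC captures such an effect only as far as ADC and payload move together.

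The documents suggest that they need not. Protocol 2 expects release after cellular uptake and linker cleavage. In the 3-month monkey study (Protocol 2.2), anti-drug antibodies lowered ADC exposure on Day 85 without affecting payload exposure, and on that day ADC rose more than in proportion to dose while payload stayed roughly proportional. These are repeat-dose animal data: they show that the two can separate, not by how much after one human dose.

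At stake is whether the trial's only exposure-response analysis of QTc can describe a payload effect, when the data for it are already being collected.

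**Working it through.** **No figure to reproduce.** The documents give no sample size, power or effect size for this analysis. Doses, cohort sizes and payload half-life are redacted, and no human payload time course is given. The check is therefore of direction, with size shown over a range of assumptions.

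**Model, from SAP 10.6.5.** ΔQTcF = intercept + θ1·treatment + θ2·concentration + categorical time + participant effects. The placebo-corrected prediction for a dose is θ1 + θ2·Cmax. Centered baseline was left out because the simulated effect does not depend on it.

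**Assumed truth.** Effect(t) = 10 ms × payload(t) / peak payload at the top dose.

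**Inputs read from the documents.** Eight cohorts; placebo pooled; 90% intervals. ECG times were read from the Part A schedule and Protocol 8.2.3 as 6, 24, 48, 96 and 144 h and about Days 15, 29 and 57.

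**Inputs assumed.** 57 active and 19 placebo participants; a 100-fold dose range; ADC terminal half-life 5 to 18 days; payload lag half-life 0.1 to 8 days; between- and within-participant SD 6 ms each.

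**Result.** Expected prediction at top-dose ADC Cmax from a random-intercept generalized least squares fit. Shortfall = 10 minus the prediction. Ranges run over the ADC half-lives.

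| Payload peak (days) | ADC model (ms) | Shortfall (ms) |
|---|---|---|
| about 0.45 | 10.8 to 11.1 | none |
| about 1.5 | 8.9 to 9.3 | 0.7 to 1.1 |
| 2.2 to 2.9 | 7.2 to 7.9 | 2.1 to 2.8 |
| 3.5 to 5.4 | 5.1 to 6.0 | 4.0 to 4.9 |
| 5.4 to 9.8 | 2.6 to 3.9 | 6.1 to 7.4 |
| 8 to 16 | 0.3 to 1.7 | 8.3 to 9.7 |

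In the 3.5 to 5.4 day row the 90% upper limit is 9.1 to 10.0 ms, at or below the true 10 ms. In the last row the concentration slope is negative.

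**Same model on payload.** The prediction at payload Cmax is 10.0 ms in every row, with an upper limit of about 13.6 to 13.8 ms. The data were generated from payload, so this is expected and is not a forecast.

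**Check with random intercept and slope, as the SAP specifies.** At ADC half-life 10 days, mean predictions on ADC were 4.9 ms (payload peak 4.5 days) and 2.7 ms (7.5 days), against 9.1 and 9.7 ms on payload. This used 25 runs per scenario, some with convergence warnings, so it supports the direction only.

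**Would the planned delay check show it?** The hysteresis plot is against ADC, pools all doses and stops at 24 h by default. By Protocol 8.2.3, IV cohorts have postdose ECGs in that window at about 6 h and 24 h, and SC cohorts at 24 h only. That shows little of a delay of several days. Active-arm ADC values below quantification are set to missing, so those ECGs leave the model even when payload is quantifiable.

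**The case against.** The strongest reply is that nothing in the documents points to a payload effect on QTc. The hERG result is reassuring, and the monkey study of the ADC included safety pharmacology with no cardiac effect among its key findings. This stands, and it makes the point an improvement rather than a defect that undermines the analysis.

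Second, a reader might infer that payload lags the ADC. The documents do not establish this. They give an expected release mechanism but no human time to peak. Slow release need not mean a late peak: a quickly cleared payload formed slowly from circulating ADC would broadly track it. The first row of the table is that case, and there the ADC model loses nothing.

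Third, a reader might call ADC the wrong exposure variable, or the result falsely reassuring. Neither follows. ADC is the dosed product, the SAP follows the protocol, and Protocol 9.3.5.1.1 presents the analysis as exploratory. No QTc threshold or exclusion claim is set, and SAP 10.6.15 plans no inferential safety analyses.

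Fourth, other safeguards exist: QTcF summaries by time point, categorical outlier counts, discretion to extend the hysteresis plot, and general permission for additional analyses. The first two do not depend on ADC concentration and could reveal a late change. None relates QTc to payload, and no alternative model is named if a loop appears. A payload model chosen after seeing the data would also carry less weight than a prespecified one.

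**Conclusion.** The point holds in conditional form. The plan models QTc on intact ADC alone, although the hERG-tested payload is measured on the same Part A schedule. If payload peaks within about half a day, nothing is lost. If a payload-driven effect peaks later, the ADC model underestimates it increasingly with delay: for a true 10 ms peak, by about 1 ms at 1.5 days, 2 to 3 ms at 2 to 3 days, and 4 to 5 ms at 3.5 to 5.4 days. These sizes rest on the assumed effect, doses, numbers, variances and kinetics; only the direction carries over to this trial. The documents do not support concluding that a payload effect exists, that payload lags in humans, or that the ADC analysis will mislead. This is a cheap improvement worth making.

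**What to change.** Keep the ADC model as planned. In SAP 10.6.5, prespecify a separate supportive model of the same form with time-matched LY3558533 concentration (0 for placebo) in place of ADC. It should not be a joint model, since the two concentrations may be nearly collinear. Report its slope, 90% CI and predicted ΔΔQTcF at the geometric mean payload Cmax of each dose. Draw the hysteresis plot over all Part A ECG visits instead of to 24 h by default.

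The cost is one more model run and a short SAP revision. No new sample, visit or assay is needed. Because values below quantification are treated as missing in active arms, low-dose cohorts may contribute few payload records; showing the number of quantifiable values per dose beside the estimates would make that limit visible.
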